3.2.1.3 Tumor markers

Tumor markers *alone* cannot be used to assess objective tumor responses. If markers are initially above the upper normal limit, however, they must normalize in order for a subject to be considered as having attained a complete response.

3.3 New lesions

The appearance of new malignant lesions denotes disease progression. The finding of a new lesion should be unequivocal: i.e. not attributable to differences in scanning technique, change in imaging modality or findings thought to represent something other than tumor (for example, some ‘new’ bone lesions may be simply healing or flare of pre-existing lesions). This is particularly important when the subject’s baseline lesions show partial or complete response. For example, necrosis of a liver lesion may be reported on a CT scan report as a ‘new’ cystic lesion, which it is not.

A lesion identified on a follow-up study in an anatomical location that was *not* scanned at baseline is considered a new lesion and will indicate disease progression. An example of this is the subject who has visceral disease at baseline and while on study has a CT or MRI brain scan ordered which reveals metastases. The subject’s brain metastases are considered to be evidence of PD even if he/she did not have brain imaging at baseline.

If a new lesion is equivocal, for example because of its small size, continued therapy and follow-up evaluation will clarify if it represents truly new disease. *If repeat scans confirm there is definitely a new lesion, then progression should be declared using the date of the initial scan.*

3.3.1 FDG-PET evaluation

While FDG-PET response assessments need additional study, it is sometimes reasonable to incorporate the use of the qualitative assessment of FDG-PET scanning to complement CT scanning in assessment of progression (particularly possible ‘new’ disease). New lesions on the basis of FDG-PET imaging can be identified according to the following algorithm:

- Negative FDG-PET at baseline, with a positive FDG-PET at follow-up is a sign of PD based on a new lesion.
- No FDG-PET at baseline and a positive FDG-PET at follow-up:
 - If the positive FDG-PET at follow-up corresponds to a new site of disease confirmed by CT, this is PD.
 - If the positive FDG-PET at follow-up is not confirmed as a new site of disease on CT, additional follow-up CT scans are needed to determine if there is truly progression occurring at that site (if so, the date of PD will be the date of the initial positive FDG-PET scan).
 - If the positive FDG-PET at follow-up corresponds to a pre-existing site of disease on CT that is not progressing on the basis of the anatomic images, this is not PD.

4 RESPONSE CRITERIA

4.1 Time point response

A response assessment should occur at each time point specified in the protocol.

For subjects who have **measurable disease** at baseline Table 4.1 provides a summary of the overall response status calculation at each time point.

Table 4.1. Time point response: subjects with target (+/- non-target) disease.

Target lesions	Non-target lesions	New lesions	Overall response
CR	CR	No	CR
CR	Non-CR/non-PD	No	PR
CR	Not evaluated	No	PR
PR	Non-PD or not all evaluated	No	PR
SD	Non-PD or not all evaluated	No	SD
Not all evaluated	Non-PD	No	NE
PD	Any	Yes or No	PD
Any	PD	Yes or No	PD
Any	Any	Yes	PD

CR = complete response, PR = partial response, SD = stable disease, PD = progressive disease, NE =not evaluable.

4.1.1 **Missing assessments and not evaluable designation**

When no imaging/measurement is done at all at a particular time point, the subject is **not evaluable (NE)** at that time point. If only a subset of lesion measurements are made at an assessment, the case is also considered NE at that time point, unless a convincing argument can be made that the contribution of the individual missing lesion(s) would not have changed the assigned time point response.

4.1.2 **Confirmation Scans**

- **Verification of Response:** *Confirmation of PR and CR is required within 4 weeks to ensure responses identified are not the result of measurement error.*

4.2 **Best overall response: All timepoints**

The *best overall response* is determined once all the data for the subject is known. It is the best response recorded from the start of the study treatment until the end of treatment taking into

account any requirement for confirmation. The subject's best overall response assignment will depend on the findings of both target and non-target disease and will also take into consideration the appearance of new lesions.

Best response is defined as the best response across all time points with subsequent confirmation. Complete or partial responses may be claimed only if the criteria for each are met at a subsequent time point as specified in the protocol (generally 4 weeks later).

In this circumstance, the best overall response can be interpreted as specified in Table 4.2. When SD is believed to be best response, it must meet the protocol specified minimum time from baseline. Measurements must have met the SD criteria at least once after study entry at a minimum interval (in general not less than 6–8 weeks) that is defined in the study protocol.

Table 4.2. Best overall response when confirmation of CR and PR IS required.

Overall response	Overall response	BEST overall response
First time point	Subsequent time point	
CR	CR	CR
CR	PR	SD, PD or PR ^a
CR	SD	SD provided minimum criteria for SD duration met, otherwise, PD
CR	PD	SD provided minimum criteria for SD duration met, otherwise, PD
CR	NE	SD provided minimum criteria for SD duration met, otherwise NE
PR	CR	PR
PR	PR	PR
PR	SD	SD
PR	PD	SD provided minimum criteria for SD duration met, otherwise, PD
PR	NE	SD provided minimum criteria for SD duration met, otherwise NE
NE	NE	NE

CR = complete response, PR = partial response, SD = stable disease, PD = progressive disease, NE = not evaluable.

^a If a CR is truly met at first time point, then any disease seen at a subsequent time point, even disease meeting PR criteria relative to baseline, makes the disease PD at that point (since disease must have reappeared after CR). Best response would depend on whether minimum duration for SD was met. However, sometimes 'CR' may be claimed when subsequent scans suggest small lesions were likely still present and in fact the subject had PR, not CR at the first time point. Under these circumstances, the original CR should be changed to PR and the best response is PR.

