Blood samples for PK, ADA, Biomarkers	See Table 5.5A for timing of samples					
Efficacy Response Assessments						
Disease assessment, Tumor Imaging (CT or MRI of Chest/Abdomen/Pelvis; MRI brain if clinically indicated)				X (between days 49-56)	X	Tumor assessments should be done every 8 wks (+/- 1 wk) until confirmed disease progression is documented or follow-up is completed. Methods used at baseline should be continued throughout study. MRI of brain are only required if clinically indicated
Clinical Drug						
Dispense Study Drug/Treatment	X	X	X	X		Nivolumab will be administered as an IV infusion on Days 1, 15, 29, 43 of each 56 day treatment cycle (8 weeks/cycle)

Table 5.1C: CA209038 Follow-up Visits - Part 1 (Cohorts 1 and 2)		
Procedure	Follow-up Visit 1 (40-60 days) and Visit 2 (101-120 days)	Notes
Safety Assessments		
Physical Examination	X	
Vital Signs (including ECOG)	X	Includes body temperature, respiratory rate, pulse oximetry, seated blood pressure and heart rate. Blood pressure, pulse oximetry and heart rate should be measured after the subject has been seated quietly for at least 5 minutes
Adverse Events Assessment	X	For study related adverse events only
Review Concomitant Medications	X	
Laboratory Tests	X	To include CBC with differential, Complete Metabolic Panel (Na, K, Cl, CO ₂ , BUN, Cr, eGFR, AST, ALT, Alk Phos, Albumin, Total Bilirubin, Total Protein, Calcium, glucose), direct bilirubin, lipase, LDH, magnesium, phosphorus, TSH
Serum or Urine Pregnancy Test	X	
ECG	X	12 Lead; for the first two follow-up visits only. Measurement should be recorded after the subject has been supine for at least 5 minutes
Tumor biopsy	X (encouraged, not mandated)	Upon confirmed progression May be done at either Follow-up visit 1 or Follow-up visit 2

Table 5.1C: CA209038 Follow-up Visits - Part 1 (Cohorts 1 and 2)		
Procedure	Follow-up Visit 1 (40-60 days) and Visit 2 (101-120 days)	Notes
Efficacy Assessments		
Disease assessment (CT/MRI)	X	Done after 12 weeks from the last on-study scan during Follow-up Visit 1 OR 2 then Q12wks by methods used at baseline Not required for subjects entering follow-up period for confirmed disease progression
Exploratory		
Blood samples for PK, ADA	X	As per Table 5.5A

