5.4 Efficacy Assessments

Disease evaluation with computed tomography (CT) and/or magnetic resonance imaging (MRI) of chest, abdomen, and pelvis, as appropriate, will be performed at baseline, and then

approximately every 8 weeks until confirmed disease progression as described in [Section 4.3.8](#) and/or completion of follow-up. Brain MRI will be performed at screening, approximately every 16 weeks thereafter, and if clinically indicated. Brain MRI will be performed approximately every 8 weeks for subjects in Arms D and E.

In the Extension Period, tumor assessments will be performed every 8 weeks (prior to dosing). CT Chest and CT or MRI abdomen, pelvis and all known sites of disease should be performed using the same imaging method used at screening. For Arms D and E only, MRI brain will also be performed (subjects in other arms who have stable brain metastases should have surveillance brain MRI approximately every 16 weeks and as clinically indicated).

Tumor response will be determined for all subjects as defined by RECIST 1.1. Individual patients will be treated according to principles that allow treatment beyond initial radiographic progression (outlined in [Section 4.3.8](#)).

At the sponsor's discretion, scans and measurements may be reviewed by independent radiologists using RECIST 1.1 criteria at a later date or any time during the study. In the absence of clinical deterioration, any initial assessment of progressive disease (PD) will be confirmed by a repeat evaluation at the next tumor assessment time point, but no sooner than 4 weeks later.

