8.3.2.2 Efficacy

The secondary objective relating to efficacy is to describe the anti-tumor activity of nivolumab and nivolumab in combination with ipilimumab in subjects with advanced melanoma. This objective will be measured by the following endpoints based on RECIST 1.1 criteria ([Appendix 2](#)). Disease evaluation will be performed at baseline, and then approximately every 8 weeks until disease progression or treatment discontinuation, whichever happens later.

The best overall response (BOR), computed for all treated subjects, is defined as the best response designation over the study as a whole, recorded between the dates of first dose until the last tumor assessment prior to subsequent therapy. CR or PR determinations included in the BOR assessment must be confirmed by a second scan performed no less than 4 weeks after the criteria

for response are first met. For those subjects who have surgical resection, only pre-surgical tumor assessments will be considered in the determination of BOR.

The objective response rate (ORR) is defined as the proportion of subjects with a BOR of CR or PR divided by the number of treated subjects (or response-evaluable subjects).

The Progression Free Survival Rate (PFSR) is defined as the probability of a subject remaining progression free or survival to time t , where $t=24$ weeks. This probability will be calculated by the product limit method (Kaplan-Meier estimates) which takes into account censored data.

The duration of response, computed for all treated subjects with a BOR of CR or PR, is defined as the time between the date of first response and the date of disease progression or death, whichever occurs first. For those subjects who remain alive and have not progressed or received subsequent therapy, duration of response will be censored on the date of last tumor assessment. For subjects who receive subsequent therapy prior to documented progression, duration of response will be censored on the date of subsequent therapy.

Progression free survival (PFS), computed for all treated subjects, is defined as the time between date of first dose of study therapy and date of progression or death, whichever occurs first.

[REDACTED]

[REDACTED]

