4.2.2 Preliminary Anti-tumor Activity

The secondary objective relating to efficacy is to describe the anti-tumor activity of nivolumab and nivolumab in combination with ipilimumab in subjects with advanced melanoma. Changes in tumor measurements and tumor response will be measured based on RECIST 1.1. Disease evaluation will be performed at baseline, and then prior to each cycle for Part 1, or prior to the

[figure not shown]
first dose of the next treatment visit for Parts 2-4, approximately every 8 weeks until confirmed disease progression or treatment discontinuation, whichever happens later. Patients will be followed for overall survival up to 2 years from the first dose of study medication or for those patients that enter the Extension Period, overall survival assessments will be continued for 100 days following the last treatment dose. The following set of efficacy study-level endpoints will be used:

[figure not shown]
- **Objective Response Rate (ORR):** The total number of subjects whose best overall response (BOR) is either a complete response (CR) or partial response (PR) divided by the total number of subjects in the population of interest (eg, all treated subjects or response-evaluable subjects).
 - Best Overall Response: The subject's best response designation over the study as a whole, recorded between the date of first study drug administration and the date of objectively documented progression per RECIST 1.1, with subsequent confirmation, or date of subsequent anti-cancer therapy, whichever occurs first in the study.
 - ◆ For those subjects who have surgical resection, only pre-surgical tumor assessments will be considered in the determination of BOR.
 - ◆ For subjects without documented progression per RECIST 1.1 or subsequent anti-cancer therapy, all available response designations will contribute to the BOR determination.
 - ◆ For subjects who continue treatment beyond progression, the BOR should be determined based on response designations recorded up to the time of the initial RECIST 1.1 defined progression.
 - ◆ For a BOR of CR or PR, the response assessment must have been confirmed by a consecutive assessment meeting the criteria for response and performed no less than 4 weeks (28 days) after the criteria for response are first met.
 - ◆ For a BOR of stable disease (SD), the following criteria will be applied to the SD derivation:

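### The best overall response window ends at three different points, so a PR after initial progression counts in the protocol but not in the SAP; one Appendix 2 sentence also inverts the 4-week confirmation rule

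*Protocol*

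**What the plan says.** **BOR window**

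- Protocol 8.3.2.2 counts response designations from first dose to the last scan before any subsequent therapy. Progression does not close the window.
- Protocol Appendix 2, section 4.2, counts from the start to the end of study treatment.
- SAP 4.2.2 closes the window at the earlier of documented RECIST 1.1 progression and subsequent anti-cancer therapy. A separate bullet for subjects treated beyond progression names the initial progression.

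Protocol 4.3.8 permits study drug after initial PD. It dates progression at that initial event in any analysis using the investigator's progression date, but gives no cut-off for BOR. The note closing SAP 4.2.2 takes BOR, response date and progression date for the final report from the case report form (CRF). Interim analyses use values derived by the sponsor.

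**Confirmation of CR and PR**

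- Appendix 2, section 4.1.2: "Confirmation of PR and CR is required within 4 weeks to ensure responses identified are not the result of measurement error".
- Protocol 8.3.2.2: a CR or PR "must be confirmed by a second scan performed no less than 4 weeks after the criteria" are first met.
- SAP 4.2.2: the response must be "confirmed by a consecutive assessment meeting the criteria for response and performed no less than 4 weeks (28 days").
- Appendix 2, section 4.2, refers back to the protocol: the criteria must be "met at a subsequent time point as specified in the protocol (generally 4 weeks later").
- Protocol 5.4, on PD rather than response, also uses a minimum: initial PD "will be confirmed by a repeat evaluation at the next tumor assessment time point, but no sooner than 4 weeks later".

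**The concern.** ORR, duration of response, time to response, disease control rate and responder status in the PD-L1 analyses all inherit BOR. Protocol 4.3.8 says a minority of subjects may benefit after initial PD, and 4.3.11 says objective responses can come after apparent radiological progression. The plan therefore admits the very sequence on which its BOR definitions disagree.

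Investigators work from the protocol and its appendix, and their CRF entry supplies the final report. A subject could be recorded as a responder under the protocol text although the SAP definition printed beside the result excludes that response. The same subject could be a non-responder in a sponsor-derived interim analysis and a responder in the final report, with no new data.

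The confirmation sentence is a second, smaller conflict. Read literally, it turns a minimum interval into a maximum, and only a scan exactly 28 days later satisfies both rules.

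**Working it through.** The plan gives no figure to reproduce here. The check compares definitions, then does date arithmetic.

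**1. Where the BOR window closes**

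| Place | Window closes at | Cut at progression? |
|---|---|---|
| Protocol 8.3.2.2 | last scan before subsequent therapy | no |
| Appendix 2, 4.2 | end of treatment | no |
| SAP 4.2.2, main clause | progression or subsequent anti-cancer therapy | yes, but a phrase on later confirmation could attach to the progression or to the response |
| SAP 4.2.2, bullet on treatment beyond progression | initial progression | yes |

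Table 4.2 in Appendix 2 has no row beginning with PD, so it does not settle the matter.

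**2. An illustrative subject (dates assumed, on the Parts 2-4 schedule)**

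Week w Day 1 is study day 7(w − 1) + 1, so weeks 7, 13, 23 and 31 are days 43, 85, 155 and 211. Suppose PD on day 43 by target-lesion growth, treatment continued, PR on days 155 and 211, and no subsequent therapy.

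- Confirmation: 211 − 155 = 56 days, which meets the 28-day minimum.
- BOR under Protocol 8.3.2.2: PR. Under Appendix 2, 4.2: PR, if treatment is still running on day 211.
- BOR under the SAP bullet: PD.
- Duration of response within the protocol alone runs from first response (8.3.2.2) to the progression date fixed by 4.3.8: 43 − 155 = −112 days, or −111 with the SAP 8.1 convention of adding one day.

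Target-lesion growth is the main route. Under Appendix 2, Table 4.1, any new lesion makes the time-point response PD, so PD through a new lesion does not become PR while that lesion persists.

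**3. Can scheduled scans meet a 4-week maximum?**

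- Parts 2-4 (Tables 5.1D and 5.1E: weeks 7, 13, 23, then every 8 weeks). The shortest nominal gap is 85 − 43 = 42 days. With the 7-day-early allowance it is 42 − 7 = 35; using the ±2-day window at both ends as well, 35 − 4 = 31.
- Part 1: "Tumor assessments should be done every 8 wks (+/- 1 wk"). Nominal gap 56 days. Scans on days 49-56 of each cycle give at least 56 − 7 = 49; one week of slack at both ends gives 56 − 14 = 42.

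Every gap exceeds 28 days, so no two consecutive periodic scans satisfy section 4.1.2, while all satisfy the minimum. Among scans marked in the schedule tables, only an end-of-treatment scan could fall inside 28 days. Table 5.1B marks one for Part 1 in the row "Disease assessment, Tumor Imaging (CT or MRI of Chest/Abdomen/Pelvis; MRI brain if clinically indicated"), and Table 5.1F marks one for the Extension Period. Tables 5.1D and 5.1E mark none.

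**4. Size of one reclassification**

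1/10 = 10 points (Arm B, D or E); 1/20 = 5 (Arm A in Part 2 or in Part 3); 1/40 = 2.5 (Cohort 1 or 2); 1/50 = 2.0 (Cohort 1 with Arm B, combined under Protocol 8.4.2); 1/150 = 0.7 (all subjects).

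The documents give no expected ORR. Assuming 30%, the exact 95% intervals are:

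| n | Base case | One more responder |
|---|---|---|
| 10 | 3/10: 6.7% to 65.2% | 4/10: 12.2% to 73.8% |
| 40 | 12/40: 16.6% to 46.5% | 13/40: 18.6% to 49.1% |

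The shifted estimates, 40% and 32.5%, lie well inside the base-case intervals.

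**The case against.** The best defence is that the documents already show what is meant. On confirmation, Protocol 8.3.2.2 and SAP 4.2.2 agree on a minimum, Appendix 2 section 4.2 defers to the protocol, and SAP 7.8.2 requires confirmed responses in the final analyses. That stands: section 4.1.2 is a drafting slip. It should still be corrected, because 8.3.2.2 sends the reader to Appendix 2 for the criteria.

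On the window, SAP 4.2.2 has an explicit bullet for subjects treated beyond progression, so the analysis rule is written down. That stands too, with two limits. The bullet is not in the text investigators follow, although their BOR is what the final report uses. And the SAP's main clause carries the unclear phrase on later confirmation, so the SAP cut-off is not unambiguous.

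It is also fair that the CRF completion guidelines and the Data Presentation Plan are not available. Either might already tell sites to stop BOR at initial PD. The documents show that a conflicting entry is possible, not that it will occur.

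Finally, the study is exploratory with a biomarker primary objective, and the SAP plans no formal inference that would need adjustment. That limits the impact but does not reconcile the text.

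**Conclusion.** The BOR window conflict is real and is the main point: it decides whether a confirmed PR after initial PD counts as a response. The confirmation conflict is a wording error of small reach. Impact is low. The affected endpoints are secondary and descriptive, the number of affected subjects cannot be derived from the documents, and the intervals above rest on an assumed 30% ORR. A 10-point shift in an arm of 10 could realistically arise only through the BOR window, because Arms B, D and E have no end-of-treatment scan marked before the Extension Period.

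A reader might infer more than the documents support:

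- **That responses after progression are expected.** Protocol 4.3.11 says only that they can occur, and 4.3.8 speaks of a minority.
- **That the plan gives one subject a PFS of 43 days and a time to response of 155 days.** Time to response is defined only in the SAP, where the subject in step 2 has BOR of PD and hence none. The pair appears only if a BOR recorded under the protocol is fed into the SAP endpoint. SAP duration of response runs to the first progression after response, so it does not give the negative value either.
- **That an early end-of-treatment scan in Part 1 would change the result.** With PR on day 52 and again on day 73, the gap is 21 days and only section 4.1.2 is met. The outcome then turns on the next scan. Table 5.1C places it "Done after 12 weeks from the last on-study scan during Follow-up Visit 1 OR 2", whereas Table 5.1B and Protocol 5.4 and 8.3.2.2 point to about 8 weeks. If that scan still shows PR, the protocol's minimum is met as well.

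**What to change.** 1. In Protocol 8.3.2.2 and Appendix 2 section 4.2, end the BOR window at the earlier of initial RECIST 1.1 progression and subsequent anti-cancer therapy. In the main clause of SAP 4.2.2, state what the phrase on later confirmation refers to, so that the clause agrees with its own bullet on initial progression.
2. In Appendix 2 section 4.1.2, require confirmation at least 4 weeks after the response criteria are first met.
3. Optionally, keep the CRF as the source of BOR for the final report, apply these two rules to the recorded time-point assessments, and list the discrepancies. This is not claimed as a gap, since the Data Presentation Plan may already cover it.

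The cost is three wording edits in the protocol, by amendment or administrative letter, and one in the SAP, with no new scans or data. The optional listing can reuse the derivation already planned for interim analyses. The downside is a few footnoted differences between CRF and derived BOR. Shrinkage after initial PD would also appear only in the tumor listings or in the optional analysis by immune-related criteria (SAP 7.5.1).
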